7.2.4 Unanticipated Problems Involving Risks to Subject or Others (UPIRSO)

A UPIRSO is a type of SAE that includes events that meet ALL of the following criteria:

- Is *unanticipated* in terms of nature, severity, or frequency
- Places the research subject or others at a different or *greater risk of harm*
- Is deemed to be *at least possibly related* to participation in the study.

7.3 Reporting of pregnancy and lactation

Although pregnancy and lactation are not considered adverse events, it is the responsibility of investigators or their designees to report any pregnancy or lactation in a subject (spontaneously reported to them), including the pregnancy of a male subject's female partner, that occurs during the trial or within 5 months after the last dose of study drug for FOCBP or 7 months for males with FOCBP partners. All subjects and female partners of male subjects who become pregnant must be followed to the completion/termination of the pregnancy. Pregnancy outcomes of spontaneous abortion, missed abortion, benign hydatidiform mole, blighted ovum, fetal death, intrauterine death, miscarriage and stillbirth must be reported as serious events (Important Medical Events). If the pregnancy continues to term, the outcome (health of infant) must also be reported.

7.4 Adverse Event Reporting

7.4.1 Routine Reporting

All routine adverse events, such as those that are expected, or are unlikely or definitely not related to study participation, are to be reported on the appropriate eCRF according to the time intervals noted in the appendices. Routine AEs will be reviewed by the Data Safety Monitoring Committee (DSMC) according to the study's phase and risk level, as outlined in the DSMP.

7.4.2 Determining if Expedited Reporting is Required

This includes all events that occur within 30 days of the last dose of protocol treatment. Any event that occurs more than 30 days after the last dose of treatment and is attributed (possibly, probably, or definitely) to the agent(s) must also be reported accordingly.

- 1) Identify the type of adverse event using the NCI CTCAE v 4.03.
- 2) Grade the adverse event using the NCI CTCAE v 4.03.
- 3) Determine whether the adverse event is related to the protocol therapy.

Attribution categories are as follows:

- Definite: AE is clearly related to the study treatment.
- Probable: AE is likely related to the study treatment.
- Possible: AE may be related to the study treatment.
- Unlikely: AE not likely to be related to the study treatment.
- Unrelated: AE is clearly NOT related to the study treatment.

- 4) Determine the prior experience of the adverse event.
Expected events are those that have been previously identified as resulting from administration of the agent. An adverse event is considered unexpected, for expedited reporting purposes only, when either the type of event or the severity of the event is not listed in:
 - the current protocol

NU Study Number: NU 16N03
BMS Study Number: CA 209-802

- the drug package insert
- the current Investigator's Brochure

7.4.3 Expedited Reporting of SAEs/Other Events

7.4.3.1 Reporting to the Northwestern University QAM/DSMC

All SAEs must be reported to the assigned QAM within 24 hours of becoming aware of the event. Completion of the NU CRO SAE Form, provided as a separate document, is required.

The completed form should assess whether or not the event qualifies as a UPIRSO. The report should also include:

- Protocol description and number(s)
- The patient's identification number
- A description of the event, severity, treatment, and outcome (if known)
- Supportive laboratory results and diagnostics
- The hospital discharge summary (if available/applicable)

All SAEs will be reported to, and reviewed by, the DSMC at their next meeting.

7.4.3.2 Reporting to the Northwestern University IRB

The following information pertains to the responsibilities of the lead site (Northwestern University). Additional participating sites should follow their local IRB guidelines for reporting to their local IRBs.

- Any death of an NU subject that is unanticipated in nature and at least possibly related to study participation will be promptly reported to the NU IRB within 24 hours of notification.
- Any death of an NU subject that is actively on study treatment (regardless of whether or not the event is possibly related to study treatment) will be promptly reported to the NU IRB within 24 hours of notification, per Lurie Cancer Center policy.
- Any death of a non-NU subject that is unanticipated and at least possibly related and any other UPIRSOs will be reported to the NU IRB within 5 working days of notification.
- All other deaths of NU subjects not previously reported, other non-NU subject deaths that were unanticipated and unrelated, and any other SAEs that were not previously reported as UPIRSOs will be reported to the NU IRB at the time of annual continuing review.

7.4.3.3 Reporting to BMS

All SAE reports (including death by any cause), regardless of attribution will be reported within 24 hours to BMS Global Safety (using the NU CRO SAE Form and referencing the BMS study number, CA 209-802). The assigned study coordinator will facilitate all reporting to BMS Global Safety and email QA a copy of the report upon completion. BMS Global Safety can be notified at:

Email Address: [contact]
[contact]

8.0 DRUG INFORMATION

8.1 Nivolumab

8.1.1 Other names

ONO-4538, BMS-936558, or MDX1106, Opdivo

8.1.2 Classification - type of agent

Human IgG4 anti-PD-1 monoclonal antibody

8.1.3 Mode of action

Nivolumab acts as an immunomodulator by blocking ligand activation of the programmed cell death 1 (PD-1) receptor on activated T cells anti-PD1.

8.1.4 Storage and stability

Nivolumab solution for infusion is a sterile, non-pyrogenic single-use, isotonic aqueous solution. Vials must be stored in a secure, limited-access location at 2 to 8 degrees C (36 to 46 degrees F) and protected from light, freezing, and shaking. The product is a clear to opalescent solution, which may contain proteinaceous and extraneous particulates. The product is intended for IV administration. The drug product can be further diluted with normal saline in IV containers made of polyvinyl chloride (PVC) or non-PVC material. Opened or accessed vials should be immediately used to prepare the infusion solution in the IV bag and the infusion solution should be immediately administered.

After preparation, store the Nivolumab infusion either:

- at room temperature for no more than 8 hours from the time of preparation. This includes room temperature storage of the infusion in the IV container and time for administration of the infusion or
- under refrigeration at 2°C to 8°C (36°F to 46°F) for no more than 24 hours from the time of infusion preparation.
- Do not freeze.

8.1.5 Protocol dose specifics

240mg q2weeks and 480mg q4weeks

8.1.6 Preparation

Nivolumab should be prepared in a laminar flow hood or safety cabinet using standard precautions for the safe handling of intravenous agents applying aseptic technique.

Visually inspect the drug product solution for particulate matter and discoloration prior to administration. Discard if solution is cloudy, if there is pronounced discoloration (solution may have a pale-yellow color), or if there is foreign particulate matter other than a few translucent-to-white, amorphous particles. Note: Mix by gently inverting several times. Do not shake.

Aseptically withdraw the required volume of nivolumab solution into a syringe, and dispense into an IV bag. If multiple vials are needed for a subject, it is important to use a separate sterile syringe and needle for each vial to prevent problems such as dulling of needle tip, stopper coring, repeated friction of plunger against syringe barrel wall. Do not enter into each vial more than once. Do not administer study drug as an IV push or bolus injection.

Nivolumab injection can be infused undiluted (10 mg/mL) or diluted so as not to exceed a total infusion volume of 120mL.

8.1.7 Route of administration for this study

Intravenous infusion. Do not administer as an IV push or bolus injection. Administer nivolumab 240 mg as an intravenous infusion over 30 (-5/+15)

NU Study Number: NU 16N03
BMS Study Number: CA 209-802

minutes and 480mg as an intravenous infusion over 60 (-10/+15) minutes through a 0.2 micron to 1.2 micron pore size, low-protein binding polyethersulfone membrane in-line filter. At the end of the infusion period, flush the line with a sufficient quantity of approved diluents.

8.1.8 Incompatibilities

No incompatibilities between nivolumab injection and polyvinyl chloride (PVC), non-PVC/non-DEHP (di[2-ethylhexyl]phthalate) IV components, or glass bottles have been observed. Nivolumab should not be infused concomitantly in the same intravenous line with other medicinal products.

8.1.9 Availability & Supply

Nivolumab will be supplied by the study as 100 mg/Vial (10 mg/mL) clear to opalescent, colorless to pale yellow liquid in 10-cc Type 1 flint glass vials stoppered with butyl stoppers and sealed with aluminum seals. May contain particles.

A supply of nivolumab may be ordered from by completing a Drug Request Form provided by BMS. The first request may take place upon screening of the first patient. The initial order should be limited to 20 vials. Allow 5 business days for shipment of drug from BMS receipt of the Drug Request Form. Drug is protocol specific, but not patient specific. All drug product will be shipped by courier in a temperature-controlled container. It is imperative that only drug product designated for this protocol number be used for this study.

Drug re-supply request form should be submitted electronically 10 business days before the expected delivery date. Deliveries will be made Tuesday through Friday. When assessing need for resupply, keep in mind the number of vials used per treatment dose, and that shipments may take 14 business days from receipt of request. Drug is not patient-specific.

8.1.10 Side effects

Related side effects reported in subjects receiving nivolumab alone were:

Very Frequent – Expected to occur in more than 20% of people (more than 20 out of 100 people): Fatigue (50%), Dyspnea (38%), Musculoskeletal pain (36%), Rash (21%), Increased AST (28%), Increase alkaline phosphatase (22%), Hyponatremia (25-38%)

Frequent - Expected to occur in 10% to 20% of people (10 to 20 out of 100 people): Pruritus (19%), Cough (17%), URI (11%), Peripheral edema (10%), Increased ALT (16%), Hyperkalemia (15%)

Not Frequent – Expected to occur in less than 10% of people (less than 10 out of 100 people): ventricular arrhythmia, iridocyclitis, infusion-related reactions, increased amylase, increased lipase, dizziness, peripheral and sensory neuropathy, exfoliative dermatitis, erythema multiforme, vitiligo, psoriasis

Deaths thought to be related to nivolumab when given alone were reported in approximately 0.5% of subjects treated (approximately 1 out 200 people).

For the most recent safety update, please refer to the current Investigator's Brochure or Study Agent Prescribing Information.

NU Study Number: NU 16N03
BMS Study Number: CA 209-802

8.1.11 Safety and monitoring plan

All participants will be carefully followed for safety. Participants are seen by their study doctor and research nurse before each dose of nivolumab every 2 or 4 weeks. Safety evaluations at this time include a physical exam, vital signs, performance status assessment, and safety laboratory tests. The study team will continuously monitor participants for treatment side effects. Participants are instructed to inform their study doctor right away if they notice or feel anything different so the study doctor can check for side effects. The study doctor may be able to provide treatment for side effects. The study doctor may temporarily hold the study drug to reduce side effects. The study doctor will permanently stop the study drug if side effects are too severe and/or long lasting. All participants will be followed for side effects for 30 days from their last dose of nivolumab. Participants with ongoing side effects will continue to be followed until resolution or stabilization of the side effects. Because it is not known if nivolumab will be effective against this type of cancer, enrollment will stop after 12 participants are treated with nivolumab if none of them have their tumors shrink..

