Up to 43 patients will be enrolled with metastatic/recurrent ACC of any site of origin with evidence of disease progression who are not candidates for curative surgical or radiation therapy. An exploratory cohort of 20 patients with non-ACC of major or minor salivary glands will be enrolled concurrently.

**The first 15 ACC patients will be assessed for safety, and ACC accrual will be terminated if ≥ 7 patients are withdrawn after <24 weeks of treatment for any reason other than withdrawal of consent. Otherwise, enrollment will continue for a total of 43 ACC patients. The exploratory cohort of 20 non-ACC MSGT's will follow an independent accrual process to ACC and will also be assessed for safety; if >2 of the first 10 non-ACC patients are withdrawn after <24 weeks of treatment, the non-ACC cohort will be closed to accrual.

[figure not shown]

NU Study Number: NU 16N03
BMS Study Number: CA 209-802

STUDY SUMMARY

Title	Phase II study of nivolumab and ipilimumab for treatment of metastatic/recurrent adenoid cystic carcinoma of all anatomic sites of origin and non-adenoid cystic carcinoma malignant tumors of the salivary gland
Version	October 6, 2022, Amendment 8
Study Design	Simon two-stage single arm multi-center phase II clinical trial
Study Center(s)	Northwestern University
Objectives	
Primary:
 
 (1) To assess median progression-free survival (PFS) as well as PFS at 6 and 12 months in patients with recurrent or metastatic adenoid cystic carcinoma treated with a combination of nivolumab and ipilimumab. 
Secondary:
 
 (1) To assess the efficacy of nivolumab and ipilimumab according to response rate (RR), disease control rate (DCR) or clinical benefit rate (CBR) at 6 and 12 months- defined as sum of CR, PR, and SD, overall survival (OS) and progression free survival (PFS) in the above population using RECIST criteria. (2) To assess the efficacy of nivolumab and ipilimumab according to ORR, DCR, PFS, and OS in the above population using immune-related RECIST (irRECIST) criteria. (3) To assess the safety and tolerability profile of nivolumab and ipilimumab therapy in the above population using CTCAE version 4.03 
Exploratory:
 
 (1) To assess the immune-related biomarkers and their association with treatment response (2) To assess activity of nivolumab and ipilimumab in non-ACC malignant salivary gland tumors (MSGTs) using OS, PFS, CBR, and ORR

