Statistical Methodology	
The main outcome is median Progression Free Survival (PFS) as well as PFS at 6 and 12 months. The optimal two-stage design to test the null hypothesis that $P \leq 0.450$ versus the alternative that $P \geq 0.650$ has an expected sample size of 24.70 and a probability of early termination of 0.654. If the drug is actually not effective, there is a 0.048 probability of concluding that it is (the target for this value was 0.050). If the drug is actually effective, there is a 0.196 probability of concluding that it is not (the target for this value was 0.200). After testing the drug on 15 ACC patients in the first stage, ACC accrual will be terminated if 7 or more patients are withdrawn from the study after <24 weeks of treatment for any reason other than withdrawal of consent (this includes PD, toxicity, intolerance etc.). If the trial goes on to the second stage, a total of 43 patients will be studied. If the total number responding (where response is defined as stable disease or better) is less than or equal to 24, the drug is rejected. An additional exploratory group of 20 patients with non-ACC MSGT will be added concurrently with ACC patients for a total samples size of 63 patients. An additional safety analysis will take place for non-ACC patients; if >2 of 10 non-ACC patients are withdrawn after <24 weeks of treatment, accrual of non-ACC patients will discontinue. Response rates and 95% confidence intervals will be calculated using exact binomial probability distributions for discrete outcomes. Progression-free survival and overall survival will be graphically depicted using Kaplan-Meier curves. Adverse events will be summarized descriptively using frequencies and percentages. Statistics will be given on type, severity, frequency and attribution of adverse events. Sample size considerations are described above.

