3.0 PATIENT ELIGIBILITY

The target population for this study is patients with metastatic/recurrent adenoid cystic carcinoma (ACC) and non-adenoid cystic carcinomas (non-ACC) of major or minor salivary glands who are not surgical or radiation candidates with evidence of disease progression. This study will be led by Northwestern University. At Northwestern University, there is no competing trial.

A total of 63 [43 patients with ACC plus 20 patients with non-ACC MSGT (exploratory group)] subjects will be needed for this trial. Approximately 2 potentially eligible patients are seen per month, and it is anticipated that at least 2 per month will be accrued. Potential patients may be referred to the Principal Investigator (PI) at Northwestern University.

Eligibility will be evaluated by the study team according to the following criteria. Eligibility waivers are not permitted. Subjects must meet all of the inclusion and none of the exclusion criteria to be registered to the study. Study treatment may not begin until a subject is registered. Please refer to Section 11 for complete instructions regarding registration procedures.

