4.5 Interim Safety Analyses

Enrollment will be paused for a safety analysis after the first 15 evaluable ACC patients have been enrolled and treated. If ≥ 7 patients have been discontinued after <24 weeks of treatment for any reason (including toxicity, progression, intolerance etc.) accrual of ACC patients will be terminated. Otherwise, the study may continue enrollment until a total of up to 43 ACC subjects are treated.

An additional 20 patients with non-ACC MSGT's will be treated as an exploratory cohort. They can be enrolled at any point throughout the study and will not count toward the 15-patient safety analysis. A separate safety analysis will take place to analyze the first 10 non-ACC patients who are enrolled and treated. If >2 patients discontinue treatment prior

NU Study Number: NU 16N03
BMS Study Number: CA 209-802

to 24 weeks (for reasons other than withdrawal of consent), accrual of non-ACC patients will discontinue.

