6.6 Response Criteria – RECIST v1.1

6.6.1 Evaluation of target lesions

Complete Response (CR): Disappearance of all target lesions. Any pathological lymph nodes (whether target or non-target) must have reduction in short axis to <10mm.

Partial Response (PR): At least a 30% decrease in the sum of the diameters of target lesions, taking as reference the baseline sum diameters.

Progressive Disease (PD): At least a 20% increase in the sum of the diameters of target lesions, taking as reference the smallest sum on study (this includes the baseline sum if that is the smallest on study). In addition to the relative increase of 20%, the sum must also demonstrate an absolute increase of at least 5 mm (0.5 cm). (Note: the appearance of one or more new lesions is also considered progressions).

Stable Disease (SD): Neither sufficient shrinkage to qualify for PR nor sufficient increase to qualify for PD, taking as reference the smallest sum diameters while on study.

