8.2.11 Safety and monitoring plan

All participants will be carefully followed for safety. Participants are seen by their study team before each dose of ipilimumab (every 2 weeks). Safety evaluations at this time include a physical exam, vital signs, performance status assessment, and safety laboratory tests. The study team will continuously monitor participants for treatment side effects. Participants are instructed to inform their study doctor right away if they notice or feel anything different so the study doctor can check for side effects. The study doctor may be able to provide treatment for side

NU Study Number: NU 16N03
BMS Study Number: CA 209-802

effects. The study doctor may temporarily hold the study drug to reduce side effects. The study doctor will permanently stop the study drug if side effects are too severe and/or long lasting. All participants will be followed for side effects for 30 days from their last dose of ipilimumab. Participants with ongoing side effects will continue to be followed until resolution or stabilization of the side effects. Because it is not known if ipilimumab will be effective against anal cancer, to enrollment will stop after 12 participants are treated with ipilimumab if none of them have their tumors shrink. Study team conferences will be held monthly or more frequently if needed.

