10.2 Sample Size and Accrual

A Simon two stage optimum Phase II design will be used ⁴⁶. The main outcome is median Progression Free Survival (PFS) as well as PFS at 6 and 12 months. The optimal two-stage design to test the null hypothesis that $P \leq 0.450$ versus the alternative that $P \geq 0.650$ has an expected sample size of 24.70 and a probability of early termination of 0.654. If the drug is actually not effective, there is a 0.048 probability of concluding that it is (the target for this value was 0.050). If the drug is actually effective, there is a 0.196 probability of concluding that it is not (the target for this value was 0.200). After testing the drug on 15 patients in the first stage, ACC accrual will be terminated if 7 or more patients are withdrawn from the study after <24 weeks of treatment for any reason other than withdrawal of consent (this includes toxicity, PD, intolerance etc.) If the trial goes on to the second stage, a total of 43 patients will be studied. If the total number responding (defined as stable disease or better) is less than or equal to 24, the drug is rejected. An exploratory group of 20 patients with MSGTs will be included in the study, in addition to the 43 patients mentioned above. They can be enrolled in any order within the total accrual of 63 patients and will not participate in statistical analysis. A separate safety analysis will take place; if >2 of the first 10 non-ACC patients are withdrawn after <24 weeks of treatment, non-ACC accrual will discontinue.

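### Sections 8.1.11 and 8.2.11 stop enrollment at 12 participants if no tumor shrinks, which contradicts the single 15-patient ACC look in the schema, summary, 4.5 and 10.2

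*Combined protocol and SAP*

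**What the plan says.** Two sets of current text govern when ACC accrual stops.

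**Drug-information sections.** Section 8.1.11 says "enrollment will stop after 12 participants are treated with nivolumab if none of them have their tumors shrink". Section 8.2.11 gives the same rule for ipilimumab, on the ground that it is not known whether the drug will be "effective against anal cancer, to enrollment will stop after 12 participants are treated with ipilimumab if none of them have their tumors shrink". Neither section defines shrinkage, the cohort the 12 come from, when they are assessed, or whether accrual pauses meanwhile.

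**Design sections.** The Study Summary (Statistical Methodology) says "After testing the drug on 15 ACC patients in the first stage, ACC accrual will be terminated if 7 or more patients are withdrawn" before 24 weeks of treatment, and 10.2 agrees. Section 4.5 says "Enrollment will be paused for a safety analysis after the first 15 evaluable ACC patients have been enrolled and treated" and applies the same count. The Study Schema adds "Otherwise, enrollment will continue for a total of 43 ACC patients". On the final test, 10.2 says "If the total number responding (defined as stable disease or better) is less than or equal to 24, the drug is rejected", and the summary uses the same definition. The non-ACC cohort has a separate look at 10 patients. None of these places mentions a look at 12 or a shrinkage criterion.

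**The concern.** The two sets differ in the number of patients (12 or 15), the criterion (tumor shrinkage or staying on treatment to 24 weeks) and possibly the population (participants or ACC patients). Both are worded as mandatory, and 11.7 requires the study to be run exactly as the approved protocol describes. No section gives precedence to one.

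The criteria can also point in opposite directions. Section 6.6.1 defines stable disease as "Neither sufficient shrinkage to qualify for PR nor sufficient increase to qualify for PD". Twelve patients with stable disease and no shrinkage are twelve successes under 10.2, but they trigger the stop in Section 8. The same data could therefore require closing accrual and continuing it. If the rule were applied, the error rates in 10.2 would no longer describe the trial.

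**Working it through.** **1. Is the 12-patient rule in the stated operating characteristics?**

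Inputs from 10.2: null rate 0.45, alternative 0.65, 15 patients in stage 1, 43 in total, drug rejected at 24 or fewer successes. Exact binomial, no look at 12, continuing if at least 8 of 15 succeed:

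- Probability of early termination (PET) = P(Bin(15, 0.45) ≤ 7) = 0.6535 (stated 0.654)
- Expected N = 15 + 28 × (1 − 0.6535) = 24.70 (stated 24.70)
- Alpha = Σ over x ≥ 8 of P(Bin(15, 0.45) = x) × P(Bin(28, 0.45) ≥ 25 − x) = 0.0481 (stated 0.048)
- Power, same sum at 0.65 = 0.8035, so beta = 0.1965 (stated 0.196)

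All four match, so the rule is not in the stated figures.

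One caution: the written rule stops at 7 or more withdrawn of 15, which means continuing only with at least 9 of 15. That boundary gives PET 0.818, expected N 20.1, alpha 0.037 and power 0.704. This is a separate mismatch, but it affects the figures below, so both boundaries are shown.

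**2. How often would the rule stop enrollment?**

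With true shrinkage rate s, P(0 of 12 shrink) = (1 − s)^12. The documents give no expected shrinkage rate for this regimen in ACC, so every s is an assumption. The 5.5% is the historical objective response rate in 1.1 (22 of 397), not an estimate for this regimen.

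**3. What would it do to the design?**

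Assume all 12 have ACC, disease control is 65%, and every patient whose tumor shrinks is also a success.

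- Success probability given no shrinkage: q = (0.65 − s)/(1 − s)
- Let A ~ Bin(12, q), B ~ Bin(3, 0.65), and k = 8 or 9
- Opposite instructions (stop at 12, continue at 15) = (1 − s)^12 × P(A + B ≥ k)
- Power with the rule = power without it − (1 − s)^12 × Σ over x ≥ k of P(A + B = x) × P(Bin(28, 0.65) ≥ 25 − x)

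Example at s = 5.5%, k = 8: 0.945^12 = 0.507; q = 0.595/0.945 = 0.630; P(A + B ≥ 8) = 0.858; opposite instructions = 0.507 × 0.858 = 0.435; power = 0.8035 − 0.391 = 0.412.

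| Assumed s | P(0 of 12) | Power, continue at ≥8 (0.80 without rule) | Opposite, ≥8 | Power, continue at ≥9 (0.70 without rule) | Opposite, ≥9 |
|---|---|---|---|---|---|
| 5.5% | 0.51 | 0.41 | 0.44 | 0.37 | 0.36 |
| 10% | 0.28 | 0.59 | 0.23 | 0.53 | 0.19 |
| 15% | 0.14 | 0.70 | 0.11 | 0.62 | 0.09 |
| 20% | 0.07 | 0.76 | 0.05 | 0.67 | 0.04 |
| 30% | 0.01 | 0.80 | 0.008 | 0.70 | 0.005 |
| 40% | 0.002 | 0.80 | 0.001 | 0.70 | 0.0004 |

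The first three rows suit a reading of shrinkage as objective response. The last three illustrate any decrease in size.

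**4. If the 12 include non-ACC patients.** Take 8 ACC at 5.5% and 4 non-ACC at 10%, 30% or 50% (the span of chemotherapy response rates in 1.1). P(0 of 12) = 0.945^8 × 0.9^4 = 0.42; 0.945^8 × 0.7^4 = 0.15; 0.945^8 × 0.5^4 = 0.04.

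**The case against.** **These are stray sentences in the drug-information section, and Section 10 plainly governs.** This is partly right. The anal cancer reference marks the 8.2.11 sentence as an apparent carry-over. The 8.1.11 copy is less certain, because its visit interval of 2 or 4 weeks fits this trial's nivolumab schedule. No section says that Section 10 prevails, and both sentences remain in Amendment 8, which updated other parts of 8.2. A likely explanation does not remove a mandatory instruction.

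**The effect may be negligible.** This stands for one reading. Section 6.6.1 speaks of shrinkage too small to be a partial response, so the word need not mean objective response. If any decrease counts, at 20% to 40%, little power is lost. If the text is a carry-over, the intended design is unaffected.

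**The assumption that every shrinking tumor is a success is not assured.** This stands. A patient whose tumor shrinks but who stops for toxicity before 24 weeks counts against the drug at the 15-patient look. The joint figures are therefore illustrative.

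**A reader might infer that the 12-patient rule cannot work in time.** Section 3.0 says "it is anticipated that at least 2 per month will be accrued", so three more patients take 3/2 = 1.5 months, about 6.5 weeks, against 12 weeks to the first scheduled scan. The documents do not support that conclusion. Section 8 says participants, and non-ACC patients enroll concurrently without counting toward the 15. With accrual in the ratio 43 to 20 (an assumption), 15 ACC patients correspond to 15 × 63/43, about 22 participants. The 10 beyond the 12th take about 5 months, or 22 weeks. In addition, 4.5 pauses after evaluable patients, which may itself require a repeat disease assessment under 6.4 and 6.8. No timing claim is made here.

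**Conclusion.** The plan is wrong as written: it contains two incompatible rules for stopping accrual and does not say which applies. This is an internal contradiction in a stopping rule, not a questionable design choice, and it should be corrected. The contradiction rests on the text alone and needs no assumed rate.

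A reader might go further and infer that the trial's power is about halved. The documents do not support that. A power of 0.41 (or 0.37 with the written boundary) requires that the rule is applied, that shrinkage means objective response, that all 12 have ACC, that the true rate is 5.5%, and that shrinkers are always successes. Under an any-decrease reading at 20% to 40%, power stays at 0.76 to 0.80 (or 0.67 to 0.70). The width of that range comes from leaving the rule undefined and is not an estimate of harm.

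**What to change.** Confirm whether a 12-participant look is intended, and reconcile 8.1.11 and 8.2.11 with the schema, summary, 4.5 and 10.2.

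- **If it is not intended:** delete the sentence from both sections and cross-refer to 4.5 and 10.2 for accrual stopping. The cost is two deletions and one cross-reference in the next amendment. The only shrinkage-based look is lost, but the 15-patient look already counts progression before 24 weeks.
- **If it is intended:** define it in 4.5 and 10.2 (what counts as shrinkage, which cohort, when it is assessed, whether accrual pauses) and restate alpha, power and PET with the look included. The cost is a short recalculation, which should use a stage-1 boundary that agrees with the written withdrawal count.
- **If 12 participants have already been treated:** record whether the rule was applied and with what result.
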